**PK SAMPLING SCHEMA 12 - COHORT 2: HD cohort with 1st Dose on non-HD day Friday**

Study Day	Day 1 - no HD FRIDAY	Day 2 – HD SATURDAY	Day 3 - no HD SUNDAY				Day 4 - no HD MONDAY	Day 5 - HD TUESDAY
PF-07321332 (nirmatrelvir)/ritonavir administration	X	X b	X				X	X b
Hours after dose a	1 - 3	At end of HD (prior to dosing)	0	0.5 - 3	4 - 8	9 - 15	0	Before and During HD
PK blood sampling (Tasso)	X c	[X d ]	X d	X c	X c	X c	X d	X d
PK blood sampling during HD (arterial and venous ports)								X c
Hematology blood sample (hematocrit)								X h
Blood:Plasma Ratio sample (venous)	X g	[X g ]	[X g ]			[X g ]	X f, g	

- a. Hours are in reference to the dose of PF-07321332 (nirmatrelvir)/ritonavir on each study day. The Day 1 dose should be taken at the clinic visit.
- b. On dialysis days, participants will take study intervention as soon as feasible after HD.
- c. Venous blood samples: HD staff to obtain PK blood samples from the HD filter arterial port and the venous port at 0 hr (prior to start of HD) and at 0, 0.5, 1, 2, 3, and 4 hours post start of dialysis.
- d. Tasso blood sample: Tasso device placed by participant, caregiver, home health provider, or other healthcare provider (as appropriate).
- e. Tasso blood samples: After dosing, Tasso device placed by participant, caregiver, home health provider, or other healthcare provider (as appropriate). Collect the consecutive PK samples within the prescribed windows with each sample taken a minimum of 2 hours apart.
- f. Blood:Plasma Ratio venous sample: Collected at 0 hr prior to start of HD.
- g. Blood:Plasma Ratio venous sample: Collected immediately before or after a Tasso sample but no longer than 15 minutes between the samples. The blood:plasma ratio sample tube is divided into 1 blood sample (in a cryovial) and, after centrifugation, 1 plasma sample (in another cryovial) (reference the Central Lab Manual). Collect blood:plasma ratio samples on Day 1 and Day 5. If one sample is missed, it may be collected on Day 2, Day 3 or Day 4. Always collect a corresponding Tasso sample for each blood:plasma ratio sample.
- h. Hematocrit: Obtain 2 hematology blood samples (hematocrit) - one at time 0 hr (venous port sample) and one time of the last PK draw (venous port sample) during HD (hematocrit needed for CLd calculations).

## 2. INTRODUCTION

PF-07321332 (nirmatrelvir), an orally administered potent and selective SARS-CoV-2 Mpro inhibitor, is currently being investigated in participants with COVID-19 and severe renal impairment.

### 2.1. Study Rationale

The purpose of this study is to evaluate the safety and PK of PF-07321332 (nirmatrelvir)/ritonavir for the treatment of adult participants with COVID-19 with severe renal impairment not on HD and on HD.

The safety and efficacy of PF-07321332 (nirmatrelvir)/ritonavir in adults was demonstrated in Study C4671005 (EPIC-HR, NCT04960202), which enrolled non-hospitalized symptomatic adults with confirmed COVID-19 with at least one risk factor for progression to severe disease. Participants who received PF-07321332 (nirmatrelvir)/ritonavir within 5 days of symptom onset had an 88% (95% CI: 75%, 94%) reduction in risk of COVID-19 related hospitalization or death.

On 22 December 2021, the US FDA granted Emergency Use Authorization to PF-07321332 (nirmatrelvir) co-packaged with ritonavir for the treatment of mild-to-moderate COVID-19 in adults and pediatric patients (12 years of age or older weighing at least 40 kg) who are at risk for progression to severe disease. The use of PF-07321332 (nirmatrelvir)/ritonavir is presently not recommended in adults with severe renal impairment due to a lack of data in this population. The safety and pharmacokinetics of PF-07321332 (nirmatrelvir) has not been studied in adult participants with COVID-19 who require HD and there is limited available data in renal impairment not on HD.

### 2.2. Background

In December 2019, COVID-19 was identified as a new, potentially fatal, respiratory infection caused by the novel coronavirus, SARS-CoV-2. The WHO declared COVID-19 a Public Health Emergency of International Concern on 30 January 2020 and further characterized the disease outbreak as a pandemic on 11 March 2020. As of 22 June 2022, at least 540 million cases have been confirmed worldwide, and at least 6.3 million deaths have occurred.

COVID-19 manifests as a wide range of illness, from asymptomatic infection to severe pneumonia, ARDS, and death. Although most (approximately 80%) cases are asymptomatic or mild, patients who are hospitalized with COVID-19 may have significant morbidity and mortality and are at increased risk of developing complications such as severe inflammation associated with elevations in proinflammatory cytokines, ARDS, acute cardiac injury, thromboembolic events, hypercoagulability, and/or kidney injury. Moreover, other comorbidities, such as hypertension, obesity, and diabetes, as well as older age and male sex increase the risk for worse outcomes.

Patients with COVID-19 may have pre-existing renal impairment due to CKD, which is known to have an estimated global prevalence of 8.5–9.8%. Renal impairment and renal replacement therapy are associated with an increased risk of infection due to comorbidities,

uremia, and skin barrier disruptions. Impairment of renal function is independently associated with an increase in susceptibility to SARS-CoV-2 infection and COVID-19 disease and subsequent risk of adverse outcomes. In one large study population-based study in England of over 17 million adults, a history of dialysis or end-stage renal failure was associated with a 3 to 4-fold increase in the risk of death from COVID-19.

There is a high unmet need for effective antiviral agents that can be used in patients with COVID-19 and severe renal impairment who are at high risk of progression to severe disease. Although there are treatments for COVID-19 which are approved under emergency use authorizations, there is limited data on the safety and PK of the treatments in patients with severe renal impairment or on HD. Remdesivir, an IV anti-viral with activity against SARS-CoV-2 which is approved for hospitalized and non-hospitalized patients with COVID-19 at high risk of progression to severe COVID-19 or death, is not recommended for patients with eGFR <30 mL/min. Molnupiravir, another anti-viral agent with activity against SARS-CoV-2, has received emergency use authorization from FDA for treatment of mild-to-moderate COVID-19 in adults at high risk for progression to severe COVID-19. The PK of molnupiravir has not been evaluated in patients with end stage renal disease or on dialysis, although a significant effect on exposure is not expected. Molnupiravir reported in the final analysis in 1433 patients with at least one risk factor for progression of COVID-19 showed 6.8% hospitalization or death in the molnupiravir group versus 9.7% in the placebo group (a 31% risk reduction).

Currently there are 2 monoclonal antibody treatments which have received EUA for outpatient use in high-risk patients affected by COVID-19. Bebtelovimab and sotrovimab both have demonstrated activity against the SARS-CoV-2 Omicron variant. Although no clinical trials have been conducted for sotrovimab and bebtelovimab in renally impaired participants, renal impairment is not expected to affect the exposure of both of these agents.

PF-07321332 (nirmatrelvir) is a potent and selective inhibitor of the SARS-CoV-2 Mpro and is being developed as an oral treatment in patients with COVID-19. An oral antiviral agent would be an easy and convenient method of drug administration without requiring attendance at a healthcare setting. Whereas mAb treatment and remdesivir need to be administered parenterally which will add additional burden on healthcare setting.

This study will provide PK and safety data for PF-07321332 (nirmatrelvir)/ritonavir in participants with severe renal impairment not on HD and on HD. PF-07321332 (nirmatrelvir) is co-administered with ritonavir, a strong CYP3A4 inhibitor, to achieve exposures sufficient to suppress viral replication through the entire dosing interval (ie, Ctrough>EC90). Ritonavir does not have any antiviral activity against the SARS-CoV-2 virus.

In published case series report of 15 HD patients with COVID-19, PF-07321332 (nirmatrelvir)/ritonavir was found to be well tolerated with no SAEs.

### 2.2.1. Clinical Overview

C4671005 (NCT04960202), a Phase 2/3, randomized, double-blind, placebo-controlled study in non-hospitalized symptomatic adult participants with a laboratory-confirmed diagnosis of SARS-CoV-2 infection, included participants 18 years of age and older with at least 1 risk factor for progression to severe disease and with a COVID-19 symptom onset of  $\leq 5$  days. The study excluded individuals with a history of prior COVID-19 infection or SARS-CoV-2 vaccination before the Day 34 visit. The primary efficacy endpoint was the proportion of participants with COVID-19 related hospitalization or death from any cause through Day 28.

In the analysis of the primary endpoint from all participants enrolled in Study C4671005, an 89% reduction in COVID-19-related hospitalization or death from any cause compared with placebo in participants treated within 3 days of symptom onset was observed; 0.7% of participants who received PF-07321332 (nirmatrelvir)/ritonavir were hospitalized through Day 28 following randomization (5 of 697 hospitalized with no deaths), compared to 6.5% of participants who received placebo and were hospitalized or died (44 of 682 hospitalized with 9 subsequent deaths) ( $p < 0.0001$ ). In a secondary endpoint, PF-07321332 (nirmatrelvir)/ritonavir reduced the risk of hospitalization or death for any cause by 88% compared with placebo in participants treated within 5 days of symptom onset; 0.8% of patients who received PF-07321332 (nirmatrelvir)/ritonavir were hospitalized or died through Day 28 following randomization (8 of 1039 hospitalized with no deaths) compared with 6.3% of patients who received placebo (66 of 1046 hospitalized with 12 subsequent deaths) ( $p < 0.0001$ ). Treatment with PF-07321332 (nirmatrelvir)/ritonavir was safe and well tolerated.

Study C4671002 (NCT05011513), is a Phase 2/3, randomized, double-blind, placebo controlled study in non-hospitalized symptomatic adults with low risk of progression to severe illness. A prespecified interim analysis of Study C4671002, which included 45% of the trial's planned enrollment, showed that the novel primary endpoint of self-reported, sustained alleviation of all symptoms for 4 consecutive days, for PF-07321332 (nirmatrelvir)/ritonavir compared to placebo, was not met. The key secondary endpoint of COVID-19-related hospitalization or death from any cause through Day 28 was also examined at the interim analysis, showing 0.6% of those who received PF-07321332 (nirmatrelvir)/ritonavir were hospitalized following randomization (2 of 333 hospitalized with no deaths), compared to 2.4% of participants who received placebo and were hospitalized (8 of 329 hospitalized with no deaths).

A Phase 1, open label, 2-part study (C4671011) to investigate the effect of stable mild (eGFR  $\geq 60$  to  $< 90$  mL/min), moderate (eGFR  $\geq 30$  to  $< 60$  mL/min), or severe (eGFR  $< 30$  mL/min and not requiring dialysis) renal impairment on the plasma and urine PK, safety, and tolerability of PF-07321332 (nirmatrelvir) has been completed. PF-07321332 (nirmatrelvir) systemic exposure increased with increasing severity of renal impairment.

Following a single 100 mg dose of PF-07321332 (nirmatrelvir) administered orally in combination with ritonavir 100 mg dose given at four scheduled time points relative to the single dose, the adjusted geometric mean (90% CI) AUCinf, test/reference ratios for renal

impairment (test) compared to normal renal function (reference) were 123.8 % (99.6%, 153.9%) for mild renal impairment, 187.4% (148.5%, 236.5%) for moderate renal impairment, and 304.49% (237.6%, 390.2%) for severe renal impairment. Adjusted geometric mean (90% CI) test/reference ratios for  $C_{max}$  were 129.78% (101.9%, 165.3%) for mild renal impairment, 138.1% (113.2%, 168.6%) for moderate renal impairment, and 148.0% (111.4%, 196.7%) for severe renal impairment participants. Regression plot of CL/F versus eGFR derived from CKD-EPI equation showed a clear trend of decreasing clearance with a decrease in renal function, with intercept of 1.83 ( $P = 0.0009$ ) and slope of 0.05 ( $P < 0.0001$ ).

PF-07321332 (nirmatrelvir)/ritonavir was generally safe and well-tolerated in both healthy and renally impaired adult participants. The number of all-causality TEAEs were similar between the mild (1 AE), moderate (1 AE) and normal renal function (3 AEs) groups. All AEs in these 3 groups were mild and not considered treatment related. A greater number of participants in the severe renal impairment group experienced TEAEs (17 AEs experienced by 5 participants in the severe renally impaired group). Of these 17 AEs, 4 (dry mouth and dysgeusia) were considered treatment related. There were 3 SAEs occurring in 1 participant in the severe renally impaired group, including 1 SAE of acute kidney injury, which resulted in study withdrawal. None of the AEs or SAEs were considered treatment related in this participant. There were no clinically meaningful laboratory findings or trends observed in this study.

The proposed dose is being developed based on internal analysis of data on file using population PK modeling. This analysis demonstrated the CL was reduced by 1/3. This was based on PK modeling using draft data from renally impaired subjects enrolled in the C467 program which included 4 subjects from Study C4671005. Of note, these participants did not experience significant safety events while on study. The data from PK modeling has supported the use of a reduced dose in severe renal impaired participants with COVID-19.

### **2.3. Benefit/Risk Assessment**

More detailed information about the known and expected benefits and risks and reasonably expected AEs of PF-07321332 (nirmatrelvir)/ritonavir may be found in the PF-07321332 (nirmatrelvir)/ritonavir IB, which is the SRSD for this study.

### 2.3.1. Risk Assessment

Potential Risk of Clinical Significance	Summary of Data/Rationale for Risk	Mitigation Strategy
	Study Intervention: PF-07321332 (nirmatrelvir)	
Dysgeusia	In Study C4671005, dysgeusia was recorded as an AE by 6% of participants receiving PF-07321332 (nirmatrelvir)/ritonavir compared to <1% of participants receiving placebo	Participants may utilize recommendations to alleviate symptoms of dysgeusia while taking treatment such as peppermint post-dose. Dosing recommendations will be provided to the participant.
Emesis	Sporadic emesis was observed at $\geq 100$ mg/kg/day of PF-07321332 (nirmatrelvir) in the 15-day NHP toxicology study.	AEs will be monitored and participants may receive antiemetics.
Hypertension	Transient increases in systolic, diastolic and mean BP were observed in pre-clinical studies. In Study C4671005 (adults at high risk for severe disease) a small imbalance in hypertension AEs (1% vs <1%) was reported.	Vital signs and all AEs will be monitored in the study.
Study Intervention: Ritonavir		
Gastrointestinal disturbances (including diarrhea, nausea, vomiting, and abdominal pain)	Frequently reported adverse reaction in patients who are HIV-positive at 600 mg BID.	Lower dose of 100 mg QD is used in this study. There is a short duration of treatment (5 days). There will be close observation of AEs. Taking study intervention with food may improve tolerability.
Neurological disturbances (eg, paresthesia, including oral paresthesia, dysgeusia, and dizziness)	Frequently reported adverse reaction in patients who are HIV-positive at 600 mg BID.	Lower dose used in this study. There will be close observation of AEs.  In addition to ongoing review of AEs by the sponsor, an E-DMC will review safety data as described in Section 10.1.5.1.
Rash (most commonly reported as erythematous and maculopapular, followed by pruritic)	Frequently reported adverse reaction in patients who are HIV-positive at 600 mg BID.	Lower dose used in this study. There will be close observation of AEs and monitoring through targeted physical exams. If needed therapeutic interventions per SoC may be provided.

PFIZER CONFIDENTIAL

Potential Risk of Clinical Significance	Summary of Data/Rationale for Risk	Mitigation Strategy
Fatigue/Asthenia	Frequently reported adverse reaction in patients who are HIV-positive at 600 mg BID.	Lower dose used in this study. There will be close observation of AEs. Fatigue (low energy or tiredness) will be assessed through collection of daily signs and symptoms and will also be assessed through targeted physical examinations when performed during the study visits.
Study Procedures		
Venipuncture will be performed during the study.	There is the risk of bleeding, bruising, hematoma formation, and infection at the venipuncture site.	Only appropriately qualified personnel will obtain the blood draw.
Tasso device will be applied only to an upper extremity that does not have a functioning HD access.	There is risk of bleeding, bruising, hematoma formation, and infection in the upper extremity and the upper extremity HD access with Tasso device placement.	Only participants undergoing HD and/or caregivers of participants on HD, who have completed training on proper placement of Tasso device on upper extremities without a functioning HD access will be permitted to apply the Tasso device.

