Participant-completed electronic diary (study intervention log)		Day 1 through Day 5							
 
The electronic diary will be provided or application downloaded to participant's own device and training completed at the Baseline visit.
 
Daily dosing will be entered in an electronic diary Days 1 through Day 5. The Day 1 dose at the site should be entered in the eDiary by the participant (or caregiver) while on site.
 
For participants who are using an eDiary provided through the study, the eDiary will be collected on Day 5, the next scheduled visit or ET visit after completion of dosing log entries on the device.
 

PFIZER CONFIDENTIAL

Visit Identifier	Screening	Baseline (Day 1)	Day 5	Day 10	Day 14	Day 21	Day 34	ET	Notes
Visit Window	Day -1 to Day 1	0 days	0 days	±1 day	±2 days	±2 days	±3 days		
Type of Visit	In-Person Site or Home Health Visit with Telehealth	In-Person Site Visit	In-Person Site or Home Health Visit	Telehealth Visit	In-Person Site, Home Health or Telehealth Visit	Telehealth Visit	In-Person Site, Home Health or Telehealth Visit	In-Person Site, Home Health or Telehealth Visit	
Investigational Site check of participant eDiary dosing entries		Day 1 through Day 5							
 
On Days 1-5, site personnel will review eDiary participant dosing entries daily on the Trial Manager portal and contact participant if not completed.
 
See Section 6.5.
 

Record HD Details (Cohort 2 only)		HD Days during Day 1 through Day 5							
 
During HD treatment, site staff should record relevant HD details on the designated CRF.
 

Retrieval of unused study intervention and empty study intervention containers			X		[X]			[X]	
 
If the Day 5 visit is conducted prior to last dose of study intervention on Day 5, empty study intervention containers, and unused study intervention should be returned at the next in-person visit (Day 14). The electronic diary should be reviewed and device should be returned if applicable.
 
See Section 6.5.
 

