Study intervention accountability			X		[X]			[X]	
 
Study intervention accountability should be performed at Day 5 visit. If Day 5 visit is prior to last dose of study intervention on Day 5, study intervention accountability can be performed at the next in-person visit (Day 14).
 
See Section 6.2.
 

Contraception check	X	X	X	X	X	X	X	X	
 
See Section 5.3.1.
 

Prior/concomitant medications	X	X	X	X	X	X	X	X	
 
All prescription and over-the-counter medications including vaccines taken by the participant within 30 days before study entry (considered prior treatment) will be recorded.
 
Concomitant therapies will be collected through the Day 34 visit.
 
See Section 6.9.
 

PFIZER CONFIDENTIAL

Visit Identifier	Screening	Baseline (Day 1)	Day 5	Day 10	Day 14	Day 21	Day 34	ET	Notes
Visit Window	Day -1 to Day 1	0 days	0 days	±1 day	±2 days	±2 days	±3 days		
Type of Visit	In-Person Site or Home Health Visit with Telehealth	In-Person Site Visit	In-Person Site or Home Health Visit	Telehealth Visit	In-Person Site, Home Health or Telehealth Visit	Telehealth Visit	In-Person Site, Home Health or Telehealth Visit	In-Person Site, Home Health or Telehealth Visit	
Adjunctive therapeutic procedures	X	X	X	X	X	X	X	X	
 
Non-drug treatments and procedures will be collected through the Day 34 visit.
 

Serious and nonserious AE monitoring	X	X	X	X	X	X	X	X	
 
AEs should be assessed by means of a telehealth visit if not feasible via an in-person visit. See Section 8.1.3.
 
See Section 8.4.
 

- Screening: Assessments indicated in brackets [X] will be performed only if needed to confirm eligibility.
- Day 1- Day 34: Assessments indicated in brackets [X] will be performed for in-person (in-clinic or home health) visits and if required per the SoA.
- Day 10 and Day 21** visits will be conducted by telehealth. Telehealth visits may be an in-person visit at the discretion of the investigator.
- Day 34 visit may be conducted by telehealth if no in-person procedures need to be performed.
- ET visit may be conducted by telehealth if no in-person procedures need to be performed or if a participant no longer wants to complete an in-person visit.

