### 8.3.1. Targeted Physical Examinations

A targeted physical examination will include, at a minimum, general appearance, abdominal exam including assessment of ascites, distension, and organomegaly, lungs and cardiovascular systems.

Investigators should pay special attention to clinical signs related to any new or previous serious illnesses.

Physical examination findings collected during the study will be considered source data and will not be required to be reported, unless otherwise noted. Any untoward physical examination findings that are identified during the active collection period and meet the definition of an AE or SAE ([Appendix 3](#)) must be reported according to the processes in Sections [8.4.1](#) to [8.4.3](#).

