#### **8.5.5. Electronic diary (eDiary)**

All participants will be provided an electronic handheld device (eDiary) or will download the eDiary application on their own device to record times of study intervention administration. **All dosing times must be entered into the eDiary by the participant (or caregiver) within 24 hours of taking the dose of study intervention.**

Participants will receive daily reminders to complete eDiary entries on their own (or by caregiver) as specified on the [SoA](#). The eDiary should be completed at approximately the same time every day.

Compliance will be monitored daily during treatment by the site staff and by the sponsor. If a participant experiences any issues with the Tasso M20 device, electronic diary entry, or study intervention, they should contact the site immediately for appropriate mitigating actions.

Noted issues with compliance will be escalated to the sponsor as per the agreed upon electronic diary review plan.

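### The risk table names daily symptom collection for fatigue and targeted exams for rash, but no visible procedure collects daily symptoms and the required exam has no skin item

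*Protocol*

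**What the plan says.** Protocol Section 2.3.1 gives a mitigation for each listed risk. For fatigue/asthenia under ritonavir it states: "Fatigue (low energy or tiredness) will be assessed through collection of daily signs and symptoms". It adds targeted physical exams and close AE observation. For rash it states: "There will be close observation of AEs and monitoring through targeted physical exams".

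The places where these measures would have to appear say the following.

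- **eDiary.** Section 8.5.5 provides the device or application "to record times of study intervention administration". The SoA (Section 1.3) agrees: "Daily dosing will be entered in an electronic diary Days 1 through Day 5".
- **Daily site check, Days 1 to 5.** In the SoA, "site personnel will review eDiary participant dosing entries daily on the Trial Manager portal and contact participant if not completed". Section 6.5 describes the same check of dosing data.
- **Targeted exam.** The minimum content in Section 8.3.1 is "general appearance, abdominal exam including assessment of ascites, distension, and organomegaly, lungs and cardiovascular systems".
- **AE monitoring.** The SoA row is marked at Screening, Days 1, 5, 10, 14, 21 and 34, and early termination, with the note "AEs should be assessed by means of a telehealth visit if not feasible via an in-person visit". The visit table has no column for Days 2, 3 or 4.
- **Day 2 telehealth.** Section 8.1.1 has the site confirm the Day 2 home Tasso collection through a telehealth visit, and Section 8.1.3 makes AE and SAE review mandatory at any telehealth visit. The SoA note on Tasso training only asks the site to consider a contact at the first home collection.

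**The concern.** A risk table tells ethics committees and regulators how each named risk will be watched, and Section 2.3.3 rests its benefit-risk conclusion partly on the measures taken to limit risk. If a named measure has no procedure behind it, that conclusion cites monitoring the study does not perform.

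There is also a measurement issue. The primary endpoints are the incidence of TEAEs and of SAEs and AEs leading to discontinuation, with about 12 participants per cohort. Fatigue is hard to classify here. Malaise is among the mild-illness symptoms in Appendix 10, and Section 10.3.1 excludes expected symptoms of the disease under study from the AE definition unless they are more severe than expected. Without a day-by-day record, that judgement on events during Days 2 to 4 depends largely on what the participant volunteers or recalls on Day 5.

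**Working it through.** The plan states no figure to reproduce. The check sets the passages side by side, then counts contacts.

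**1. Is there a daily collection of signs and symptoms?**
- The eDiary holds dosing entries and dose times (Section 8.5.5; SoA). No symptom item is described.
- The daily site check covers dosing entries, and contact follows only if they are incomplete (SoA), or if noncompliance with dosing entries is suspected or observed (Section 6.5).
- The SAP safety endpoints and summaries (Sections 3.5 and 6.6) contain no symptom dataset or table.
- Result: no matching procedure, form or analysis in the readable text. Some SoA and endpoint rows are redacted and could in principle hold a symptom item, but the eDiary text is readable and names dosing only.

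**2. Does the exam cover rash?**
- Required content is general appearance, abdomen, lungs and cardiovascular systems: 0 skin items.
- The list is a floor, so a skin check is allowed but not required.
- After the first dosing day, the exam is fixed at Day 5. At Days 14 and 34 and early termination it depends on the visit being in person.

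**3. On how many of the 5 dosing days is there an AE contact?**

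| Source | Days with AE contact | Count |
|---|---|---|
| SoA alone | 1, 5 | 2 of 5 |
| SoA plus Sections 8.1.1 and 8.1.3 | 1, 2, 5 | 3 of 5 at best |

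The Day 2 contact is uncertain for two reasons. Section 8.1.1 states it as a site task, whereas the SoA note leaves it to the site's consideration. It is also tied to a Day 2 home Tasso sample, and PK Sampling Schemas 2 to 7 (Cohort 2, first dose on a dialysis day) have no Day 2 Tasso sample. Days 3 and 4 have no required AE contact under either count.

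**4. What could a missed event do to the primary summary?**
- Protocol Section 9.3.2 and SAP Section 6.1.1.1 count participants, not events.
- A missed TEAE changes overall incidence only if that participant has no other recorded TEAE.
- In that case: 1/12 = 8.3 percentage points in one cohort, and 1/24 = 4.2 points for both cohorts combined.
- If the participant has another TEAE, the change in overall incidence is 0, although the count for that event type is still too low.

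**The case against.** The best defence is that the AE process exists and this is a stray phrase. Both risk rows also cite close AE observation, and the fatigue row separately cites exams. All spontaneously reported AEs are recorded (Section 8.4.1.2). Participants with a problem with study intervention are told to contact the site at once (Section 8.5.5), and telehealth visits must include a reminder to report health changes. General appearance is on the exam list, and a competent examiner would probably notice a marked rash. Much of this stands and softens the consequence. It does not supply the daily collection the table names, nor make a skin check part of the exam the table relies on.

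A reader might infer four stronger points that the documents do not support.

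- **That no AE contact exists on Days 2 to 4.** This is true of the SoA, but Sections 8.1.1 and 8.1.3 together can give one on Day 2.
- **That exposure is near its highest on Days 2 to 4.** Nothing in the documents shows this. As a rough check, take the single-dose half-life of 13.37 h (Protocol Table 1, participants not on dialysis) and assume one compartment with instantaneous absorption. The fraction left after 24 h is 2^(−24/13.37) = 0.288. Relative to the Day 1 peak from 300 mg, Day 2 is (150 + 0.288 × 300)/300 = 79%, and the same recursion gives 73% on Day 3 and 71% on Day 4. Days 2 to 4 would equal Day 1 only with a half-life of about 24 h; no half-life on dialysis is given.
- **That the regimen is wholly untried on hemodialysis.** The synopsis and Section 2.1 say nirmatrelvir has not been evaluated in this group, but Sections 2.2 and 4.3 cite 15 treated hemodialysis patients, so the point should not rest on novelty.
- **That Cohort 2 is covered because dialysis staff see participants between Days 1 and 5.** No AE assessment is specified at those sessions.

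**Conclusion.** The point holds in a limited form. One mitigation in Section 2.3.1, daily collection of signs and symptoms, has no visible procedure. Another, exams for rash, depends on an exam whose required content has no skin item. AE contact is required on 2 of 5 dosing days by the SoA; Day 2 is uncertain, and Days 3 and 4 have none. It would go too far to say that the two mitigations do not exist, because AE observation and scheduled exams are real.

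The effect on the primary summary is bounded rather than estimated: 8.3 points per participant in a cohort, and only where that participant's sole TEAE is missed. The documents give no basis for saying how often a recall gap of at most four days would cause this. The conclusion assumes that no redacted row contains a daily symptom item. The mismatch is worth correcting because the table states a safety measure the study does not appear to carry out, and the correction is small.

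**What to change.** 1. Add one open, nonleading daily question to the Day 1 to 5 eDiary, with no symptom named, for example *any change in how you feel since yesterday?* Naming tiredness would conflict with the nonleading approach in Sections 8.4 and 8.4.2. Have the site review any positive answer under the existing AE definition, including the Section 10.3.1 rule on expected COVID-19 symptoms.
2. Add skin to the minimum exam content in Section 8.3.1.
3. Reconcile the SoA Tasso training note with Section 8.1.1 on whether the Day 2 telehealth contact is required, and state whether it applies to participants with no Day 2 Tasso sample.
4. If either of the first two additions is not made, remove the corresponding mitigation from Section 2.3.1.

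The cost is minor eDiary reprogramming, some follow-up calls after positive answers, and short text edits. Sites already open the diary data daily, so no new visit is needed. Item 4 on its own is a text edit only; it would make the protocol consistent but would not improve AE capture.
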